### 5.3.1.3 *Progression to Severe Disease or Death within 35 days of First Dose or Randomisation*

Severe disease is defined by the OSCi as a score between 5 and 7. Death is defined by an OSCi score of 8. Any patient with an OSCi score at any post baseline assessment up to and including Day 35 of 5 or more will be considered as progressed to severe disease or death.

All patients should have an OSCi score of 4 at baseline, however in the event a patient is randomised with an OSCi score of  $\geq 5$  at baseline this patient will be excluded from all analyses of progression to severe disease or death.

Day 35 will be determined by the study schedule, which may be more than 35 days after randomisation if randomisation occurs before Day 1.

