6.14 Concomitant Medications

Medications taken by the patient at the time of informed consent should be recorded in the source data. After this, patients will be asked at each visit if they have taken any new concomitant medications or changed any current medications. Alternatively, information can be obtained from the patient's hospital prescription record. The dosage information, dates of administration and reasons for use will be recorded.

Any other medications which are considered necessary for the patient's welfare should be given at the discretion of the Investigator.

Special care will be taken in questioning the patients on any possible self-medication.

SOC medications for the treatment of COVID-19 (e.g. remdesivir or dexamethasone) can be administered, as required. SOC should be recorded as concomitant medications.

Oxygen therapy will be recorded as concomitant medication.

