7.3 Serious Adverse Event

An SAE, according to ICH GCP, is any AE that meets any of the following outcomes:

- Results in death.
- Is life-threatening (i.e. at immediate risk of death).
- Requires in-patient hospitalisation or prolongation of existing hospitalisation.
- Results in persistent or significant disability or incapacity.
- Consists of a congenital anomaly or birth defect.

AEs that may not result in death, may not be life-threatening, or do not require hospitalisation may be considered SAEs when, based upon appropriate medical judgment, they may jeopardise the patient or may require medical or surgical intervention to prevent one of the outcomes listed above. These events must be reported in the same manner as SAEs.

Deterioration of a patient's condition requiring admission to the intensive care unit or invasive mechanical ventilation, (whichever happens first) must be reported as an SAE.

Elective and pre-planned surgeries will not be reported as SAEs. Such procedures should be recorded as part of the medical history.

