### 5.3.1.4 *Progression to Intubation or Death within 35 days of First Dose or Randomisation*

Intubation is defined by the OSCi as a score between 6 and 7. Death is defined by an OSCi score of 8. Any patient with an OSCi score at any post baseline assessment up to and including Day 35 of 6 or more will be considered as progressed to intubation or death.

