#### 5.3.1.5 *Death within 35 days of First Dose or Randomisation*

Deaths will be identified by an OSCi score of 8 at any post baseline assessment up to and including Day 35, a fatal Adverse Event (AE) on or before Day 35 or withdrawal due to a fatal AE on or before Day 35.

Patients who die after Day 35 will be considered alive for the derivation of death within 35 days of first dose or randomisation.

Day 35 will be determined by the study schedule, which may be more than 35 days after randomisation if randomisation occurs before Day 1.

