## 7.3 Missing Data

### 7.3.1 OSCi

#### 7.3.1.1 General Imputation Rules

For analyses using the OSCi, including the primary and key secondary endpoints, subjects with an OSCi score of 8, indicating death, will have any subsequent missing OSCi assessments set as 8. In addition, if other data sources such as AEs indicate a patient has died all missing OSCi scores on and after the date of death will be set as 8. Any missing baseline OSCi scores will be imputed as 4, as per the study inclusion criteria.

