#### 7.3.1.3 Imputation Rules for Binary Endpoints

Key secondary analyses will use the available data. Therefore, for subjects who withdraw from the study prior to day 35 this assumes that any progression to severe disease, intubation or death can only occur prior to study withdrawal. This assumption will be tested by using multiple imputation methods to impute the missing data. Further details are given in [Section 9.2.1.3](#).

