**Table 14: Intercurrent events and policies for the key secondary estimand of progression to severe disease or death**

Intercurrent event	Policy
Death	Composite variable: The definition of the endpoint includes patients who die within 35 days of first dose, regardless of their OSCI assessments.
Premature treatment discontinuation and missed doses	Treatment policy: Severe disease will be determined regardless of treatment discontinuation and the number of missed doses.
Withdrawal from study	While-on-study: Patients will only be considered having severe disease if observed and recorded whilst participating in the study. This assumes the treatment effect is independent to reason for study withdrawal.
Other protocol deviations and concomitant medications affecting efficacy	Treatment policy: Severe disease will be determined regardless of any concomitant medication use or protocol deviations.

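### A patient alive at Day 35 with no OSCI score during a recorded spell of ventilation or high-flow oxygen counts as not progressed, because missing OSCI is completed from other records for death only

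*SAP*

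**What the plan says.** **Progression.** SAP 5.3.1.3 states: "Any patient with an OSCi score at any post baseline assessment up to and including Day 35 of 5 or more will be considered" to be an event for this endpoint. SAP 5.3.1.4 has the parallel rule for intubation or death: "Any patient with an OSCi score at any post baseline assessment up to and including Day 35 of 6 or more will be considered" to be an event there. Neither section names a second data source.

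**Missing scores.** SAP 7.3.1.3 says: "Key secondary analyses will use the available data". The only rule in SAP 7.3.1.1 that draws on other records concerns death: "if other data sources such as AEs indicate a patient has died all missing OSCi scores on and after the date of death" are set to 8. SAP 5.3.1.5 likewise identifies deaths from an OSCI score of 8 or from "a fatal Adverse Event (AE) on or before Day 35 or withdrawal due to a fatal AE on or before Day 35".

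**Other records of the same events.** Protocol 7.3 says that a deterioration "requiring admission to the intensive care unit or invasive mechanical ventilation, (whichever happens first) must be reported as an SAE". Protocol 6.14 says: "Oxygen therapy will be recorded as concomitant medication".

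**Collection.** Protocol 6.6 asks for one OSCI assessment a day until Day 35. A footnote to the Study Schedule keeps OSCI among the key data for patients who stop dosing, with ventilation as its example, but only where this can be done.

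**The concern.** OSCI levels 5 to 7 are defined by the care received: non-invasive ventilation or high-flow oxygen, intubation with mechanical ventilation, and ventilation with added organ support. A dated record of that care is therefore direct evidence of the score. The plan accepts such evidence for death. For sustained discharge, SAP 5.3.1.1 uses the patient's location when OSCI is missing. It has no equivalent for scores 5 to 7, and the protocol accepts gaps in OSCI once a patient is ventilated, which is when these events occur.

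Two formally tested key secondary endpoints are affected. An event missed in this way is scored as a good outcome, not as missing. If the same fraction of events is lost in both arms, the risk difference shrinks by that fraction.

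**Working it through.** The plan gives no event rate, power or OSCI missingness for these endpoints, so there is no figure to reproduce. The check is of the rules, followed by simple arithmetic.

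**1. What happens when OSCI is missing**

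- Death: completed from AEs (SAP 5.3.1.5 and 7.3.1.1).
- Sustained discharge: confirmed from the patient's location (SAP 5.3.1.1).
- Severe disease (score 5 or more) and intubation (score 6 or more): no rule (SAP 5.3.1.3, 5.3.1.4, 7.3.1.1). With available data only (SAP 7.3.1.3), a survivor with no recorded score at that level is a non-event.

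**2. When a patient is actually missed.** All of these must hold:

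- every OSCI score during the episode is missing, since one recorded score at the level is enough;
- the patient does not die by Day 35, since such deaths are counted anyway;
- the missing scores are not recovered through the data queries in Protocol 9.2.

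**3. What the other records can show**

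- The mandatory SAE covers intensive care admission or invasive ventilation, whichever comes first. It does not name non-invasive ventilation or high-flow oxygen.
- An SAE raised for intensive care admission need not show a later intubation, and intensive care admission is not itself an OSCI level.
- For OSCI 5 the second source is therefore mainly the oxygen record. The protocol does not say that the mode of delivery is captured.

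**4. Whether the planned sensitivity analyses catch it (SAP 9.2.1.3)**

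- The tipping-point and jump-to-reference analyses address missing data due to withdrawal. They impute from a model and do not use the recorded ventilation.
- The completer analysis requires no withdrawal before Day 35 and one assessment in Days 31 to 35. A ventilated survivor with an earlier gap and one late score stays in it as not progressed.

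**5. Size**

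- One missed event in one arm: 1/305 = 0.33 percentage points. Three give 3/305 = 0.98, and five give 5/305 = 1.64.
- Effect on the risk difference (placebo minus SNG001): it falls by (missed in placebo − missed in SNG001)/305. Equal counts leave it unchanged. Loss of an equal fraction shrinks it by that fraction.

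For scale only, assume true rates and a detected fraction s that is the same in both arms. Observed difference = s × true difference. Power is for a two-sided 0.05 comparison of two proportions with n = 305 per arm: Φ{[d − 1.96√(2p̄(1−p̄)/n)] / √[(p₁(1−p₁)+p₂(1−p₂))/n]}.

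- 15% v 9%, s = 1: d = 6.0 points, p̄ = 0.12. (0.06 − 1.96 × 0.02632)/0.02620 = 0.32, power 62.6%.
- 15% v 9%, s = 0.95, 0.90, 0.80: d = 5.7, 5.4, 4.8 points; power 60.1%, 57.5%, 52.1%.
- 10% v 6%, s = 1 to 0.80: d = 4.0 to 3.2 points; power 44.4% to 36.5%.
- 20% v 13%, s = 1 to 0.80: d = 7.0 to 5.6 points; power 64.5% to 53.3%.

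None of these rates or fractions comes from the documents. The illustration also applies the loss to all events, including deaths, which cannot be lost in this way, so it overstates the effect at any given s.

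**The case against.** The strongest reply is that OSCI is the endpoint. The protocol defines progression by an OSCI score of 5 or above, or 6 or above, and the SAP implements that definition. OSCI is scored daily, preferably by a doctor or nurse, and in hospital it rests on treatment status, so the patient need not respond. SAP 7.3.2 imputes missing breathlessness from an OSCI score of 5 or more at the same assessment, so the plan expects scores to exist for such patients. The failure thus needs an unlikely chain of gaps. These endpoints are tested only if both primary endpoints succeed (SAP 7.6). Adding oxygen or ventilation records on days that already have a score would also change a protocol-defined endpoint, by counting brief episodes between daily assessments.

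Much of this stands. It limits the size of the problem and rules out a broad remedy. It does not answer the narrow case in which the score is missing and the care is documented, which the plan resolves for death but not here.

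A reader might infer three stronger points that the documents do not support:

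- **That the derivation is narrower than the estimand.** Table 14 says "Patients will only be considered having severe disease if observed and recorded whilst participating in the study", but this is the policy for withdrawal from study. It does not settle which data sources count.
- **That the database already holds all the lost events.** The limits of the SAE and oxygen records in step 3 of the working show otherwise.
- **That the treatment comparison is biased.** If there were no true effect, a true rate of 10% to 20% and 80% detection in one arm against full detection in the other would create a false difference of 2 to 4 points. But the trial is double-blind, and nothing in the documents points to different OSCI completeness by arm.

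**Conclusion.** The gap is real but narrow. The rules classify a patient as not progressed when that patient is alive at Day 35, has no OSCI score during the whole of a documented period of ventilation or high-flow oxygen, and has no qualifying score at another time. None of the planned sensitivity analyses uses the documented care to correct this.

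The frequency is unknown and cannot be derived from the documents. The one firm figure is 0.33 percentage points per missed event in an arm of 305. The likely direction is dilution, if similar fractions are lost in both arms. A bias between arms is possible in principle but is not shown. This is an optional improvement that the study team should consider, not an error that invalidates the key secondary analyses.

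**What to change.** Extend SAP 7.3.1.1, with cross-references in 5.3.1.3 and 5.3.1.4, to say that for the two progression endpoints:

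- On a day with a missing OSCI score, up to Day 35 and while the patient is on study, a dated SAE or oxygen/ventilation record that explicitly shows non-invasive ventilation or high-flow oxygen sets the score to 5. One that shows intubation or mechanical ventilation sets it to at least 6.
- Intensive care admission alone does not count, and recorded OSCI scores are never overridden.
- Qualifying records are identified by blinded medical review before unblinding.
- The number of events is reported by source and arm, and the analysis is repeated with OSCI-only events as a sensitivity analysis.

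If the team prefers to leave the main derivation untouched, the minimum is to use the supplemented derivation as the sensitivity analysis.

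The cost is a small SAP change, an entry in SAP Section 15, and one blinded listing review of the kind that SAP 8.4 and 8.5 already plan for comorbidities and COVID-19 medications. No new data are needed. The drawback is that oxygen records may not always state the mode of delivery, so some episodes will remain unclassifiable.

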The third key secondary estimand will be the difference in probabilities for SNG001 versus placebo for death within 35 days of first dose (or randomisation date if the patient is not dosed) of patients in the ITT population. For both the second and third key secondary endpoints the same policies will be used for handling intercurrent events as progression to severe disease or death.

Interim Analyses

An unblinded interim analysis will be conducted by an independent team if it is feasible for the interim data to be analysed and interpreted within a timeframe which is ethical and of scientific value to the study. If feasible, it is planned to assess futility on the first 300 randomised patients once all of these patients have completed the Day 35 visit or have withdrawn from the study. The primary analyses for the two primary endpoints will be conducted for the interim analysis and provided to an Independent Data Monitoring Committee (IDMC).

Study Schedule

Assessment	Pre-Treatment ¹	Treatment Phase ²	End of Treatment	Follow-up		
	Day 0	Days 1 to 14	Day 15	Day 16 to Day 28	Day 29 to Day 35	Day 36 to Day 90
Informed consent	X					
Inclusion / Exclusion criteria	X					
Medical history	X					
COVID-19 infection history ³	X					
Patient demographics	X					
Physical examination ⁴	X ⁵	X ^{5, 6}	X ^{5, 6}			
Height and weight	X					
WHO Ordinal Scale of Clinical Improvement ⁴	X	X ^{7, 8}	X ^{7, 8}	X ^{7, 8}	X ^{7, 8}	
BCSS	X	X ^{7, 8}	X ^{7, 8}	X ^{7, 8}		X ^{7, 8, 9}
Vital signs ^{4, 10}	X	X ⁶	X ⁶			
NEWS2 ¹¹	X	X ⁶	X ⁶	X ⁶		
EQ-5D-5L	X ¹²	X ^{7, 8, 14}	X ^{7, 8, 12, 13}	X ^{7, 8, 14}	X ^{7, 8, 14}	X ^{7, 8, 9}
COVID-19 symptom assessment		X ^{7, 8}	X ^{7, 8}	X ⁷	X ^{7, 8}	X ^{7, 8, 9}
Long-COVID-19 assessments			X ^{7, 8}	X ^{7, 8, 15}		X ^{7, 8, 9}
Urine pregnancy test (if applicable)	X					
Device training (if required)	X	X				
Randomisation	X					
Blood samples for immunogenicity test ¹⁶	X					X ¹⁷
Dose administration		X ¹⁸				
Recording of AEs and SAEs ¹⁹	X	X ^{7, 8}	X ^{7, 8}	X ^{7, 8}	X ^{7, 8}	X ^{7, 8, 20}
Recording of concomitant medications	X	X ^{7, 8}	X ^{7, 8}	X ^{7, 8}	X ^{7, 8}	X ^{7, 8}
CCI		X ²²				

1. Dosing may start on the same day as the pre-treatment assessments and if so the Day 1 assessments will not be performed.
2. All assessments and sampling are to be carried out pre-dose.
3. To include symptoms experienced within the preceding 24 hours and SARS-CoV-2 variant information (if available).

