5.3 Study Visits

5.3.1 Pre-Treatment

The following assessments should be performed on Day 0 prior to the first dose preferably in the following order:

- Informed consent
- Inclusion/exclusion criteria
- Medical history
- COVID-19 infection history (SARS-CoV-2 variant information to also be collected if available)
- Patient demographics
- Physical examination (chest examination only unless a physical examination is deemed necessary by the Investigator)*
- WHO OSCI*
- Height and weight
- Vital signs (to include temperature, respiratory rate, heart rate and blood pressure)*
- BCSS
- NEWS2 (the highest NEWS2 score for each calendar day should be collected)
- EQ-5D-5L (complete questionnaire)
- Height and weight
- Urine pregnancy test, if applicable
- Check the patient will be able to use the nebuliser
- Randomisation
- Blood sample for immunogenicity test (all sites/patients, where collection is feasible)
- Recording of AEs, SAEs and concomitant medications

*Physical examination, WHO OSCi, and vital signs assessments should be conducted together at approximately the same time each day.

Eligibility to enter the study may be aided with data captured from SOC procedures and tests performed as part of the admission process.

Patients may take the first dose of study medication either on the same day as the pre-treatment assessments or the next day depending on timings. Day 1 is the day the first dose of study medication is taken. If Day 1 is the same as the day the pre-treatment assessments are performed then the Day 1 assessments do not need to be repeated.

5.3.2 Days 1 to 14

The following assessments should be performed daily from Day 1 to 14.

For patients that remain in hospital the following assessments should be performed preferably in the following order:

- WHO OSCI*
- Physical examination (chest examination only unless a physical examination is deemed necessary by the Investigator)*
- Vital signs (to include daily temperature, respiratory rate, heart rate and blood pressure)*
- BCSS
- EQ-5D-5L (complete questionnaire on Day 7 only. Mobility, self-care and usual activities dimensions from Day 1 to Day 14)
- COVID-19 symptom assessment
- NEWS2 (the highest NEWS2 score for each calendar day should be collected)
- Device training (if required)
- Administration of study medication
- Recording of AEs, SAEs and concomitant medications.

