8.5 Statistical Analysis Methodology for Efficacy Endpoints

A SAP will be completed prior to study unblinding and database lock.

All collected data will be summarized using descriptive statistics. Summary statistics will consist of the number of observations, mean, standard deviation, minimum, median, and maximum for continuous parameters, and number and percent of subjects for categorical parameters. Changes respective to Baseline will also be evaluated where applicable. Baseline is defined as the last assessment prior to first dose.

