### 5.3 Derived variables

Unless otherwise specified, baseline is defined as the last non-missing pre-treatment assessment prior to first dose. For patients who are randomised but do not receive any study treatment baseline will be defined as the pre-treatment assessment.

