## Statistical Analysis Plan (RotW)

Final v1.0, 08FEB2022

SG018

All patients should have an OSCi score of 4 at baseline, however in the event a patient is enrolled with an OSCi score of  $\geq 6$  at baseline this patient will be excluded from all analyses of progression to intubation or death.

Day 35 will be determined by the study schedule, which may be more than 35 days after randomisation if randomisation occurs before Day 1.

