#### **9.2.1.3 Sensitivity Analyses of the Key Secondary Estimand**

The sensitivity of the key secondary analysis to missing data due to withdrawal from study prior to progression to severe disease or death will be assessed firstly through a tipping point analysis for a range of sensitivity parameters,  $\delta_i$ , for each  $i^{\text{th}}$  patient.  $\delta_i$  represents the change to the odds of severe disease or death. If  $\delta_i$  is set to 1 this will represent a Missing at Random (MAR) approach, if  $\delta_i < 1$  the imputed OSCi score will be lower than that of the MAR approach and progression to severe disease will be less common. If  $\delta_i > 1$  the imputed OSCi score will be higher than that of the MAR approach and progression to severe disease will be more common. Values of  $\delta$  will be varied independently for each treatment group.

Missing data will be imputed in M datasets. OSCi will be considered a categorical variable and the imputation algorithm will use a monotone logistic regression method to impute missing OSCi scores. Each of the covariates used in the primary analysis, including treatment group, will be included as covariates in the logistic regression. Missing data will be imputed iteratively by day, starting at day 2. For each subsequent day, the OSCi scores at prior days will be included as covariates, including the OSCi scores imputed in earlier iterations. This will not include the OSCi score at day 1 because this will always be 4, by design. However, because there are 34 scheduled visit days to be imputed in this way it is likely as the imputation progresses that the imputation model will become over-parameterised. To avoid this issue and to account for the fact that the most recent days are most likely to be predictive, only the OSCi score at the previous two days will be used as continuous covariates. Any imputations of 8 (death) will be “carried forward” to all future missing days after each step and not imputed again.

For each imputed dataset and for each value of  $\delta_i$  the primary analysis method will be repeated. The estimates from the imputed datasets will be combined for each value of  $\delta_i$  using Rubin’s rules. The results for the different combinations of  $\delta_i$  for Placebo and SNG001 patients will be plotted on a heat map to identify, if applicable, where the p-values becomes insignificant. This ‘tipping point’ will also be tabulated along with specific values of  $\delta_i$ .

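### The baseline OSCI that triggers exclusion from the severe-disease and intubation analyses is tied to first dose, so read literally it can drop patients who worsen after randomisation

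*SAP*

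**What the plan says.** **Baseline.** SAP 5.3 states that, unless otherwise specified, "baseline is defined as the last non-missing pre-treatment assessment prior to first dose". Protocol 8.5 agrees: "Baseline is defined as the last assessment prior to first dose". For undosed patients SAP 5.3 adds: "For patients who are randomised but do not receive any study treatment baseline will be defined as the pre-treatment assessment".

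**Timing.** Protocol 5.3.1 places randomisation among the Day 0 procedures, makes Day 1 the day of first dose, and lets the first dose be taken "either on the same day as the pre-treatment assessments or the next day depending on timings". Footnote 2 to the Study Schedule says of the treatment phase: "All assessments and sampling are to be carried out pre-dose". Day 1 assessments are skipped only when dosing falls on the pre-treatment day.

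**Exclusions.** For a score of 5 or more, SAP 5.3.1.3 reads "at baseline this patient will be excluded from all analyses of progression to severe disease or death". For 6 or more, SAP 5.3.1.4 reads "at baseline this patient will be excluded from all analyses of progression to intubation or death". Only post-baseline scores count as events for either endpoint. SAP 5.3.1.5 (death) has no such exclusion.

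**Population.** SAP 9.2.1.1 and 9.2.2.1 state both estimands for the ITT population, which SAP 7.1.1 defines as all randomised patients.

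**Day 1 score.** On the imputation model, SAP 9.2.1.3 says: "This will not include the OSCi score at day 1 because this will always be 4, by design".

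**The concern.** Eligibility fixes OSCI at 4 when the patient is randomised. It does not fix the score on the following day. For a next-day starter, the Day 1 pre-dose score is taken after randomisation and, being the last one before first dose, becomes the baseline. A safeguard apparently written for patients enrolled in error can then act on a post-randomisation outcome.

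At stake are the first two key secondary endpoints. Read literally, membership of an ITT analysis would depend on what happened after randomisation. A patient excluded from the severe-disease composite would be lost from it even after a later death. The same deterioration would be handled in opposite ways according to whether a dose followed. The protocol's estimand (Protocol 8.4.2) contains no such exclusion, and SAP Section 15 does not list it among the changes.

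**Working it through.** The plan gives no event rate or power for these endpoints, so there is no stated figure to reproduce. The check is to apply the definitions to individual patients and then bound the number affected.

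**Applying the definitions.** Take patients randomised on Day 0 at OSCI 4.

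| Patient | Baseline OSCI | Severe disease or death |
|---|---|---|
| Dosed on Day 0, at 5 the next day | 4 (Day 0) | Event |
| At 5 the next day, never dosed | 4 (Day 0, SAP 5.3) | Event |
| At 5 at the Day 1 pre-dose assessment, then dosed | 5 (Day 1) | Excluded, even if the patient later dies |

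Only the third patient is affected. Three conditions must all hold: a next-day start, deterioration before the dose, and a dose given afterwards.

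The third condition can occur. Protocol 4.5 does not permit administration during high-flow nasal oxygen, but allows such patients to be dosed on low-flow delivery if tolerated. It is probably uncommon:
- SAP 8.6 names an OSCI score of 5 or above as a reason for missed doses.
- Study Schedule footnote 8 gives becoming ventilated as an example of stopping dosing.
- SAP 7.3.3 refers to dosing within 24 hours of consent, so the interval is short.

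Few intubated patients would take a first dose through a mouthpiece nebuliser, so the 6-or-more branch is likely close to empty.

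**Number affected.** Expected exclusions = 610 × share starting next day × share reaching 5 or more before dosing × share still dosed. Only 610 is in the documents; the other inputs are assumptions.
- Low: 610 × 0.25 × 0.01 × 0.10 = 0.2
- Middle: 610 × 0.50 × 0.02 × 0.30 = 1.8
- High: 610 × 0.75 × 0.04 × 0.50 = 9.2

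**Effect on the comparison.** As an illustration inside that range, suppose 1% of each arm is caught (610 × 0.01 = 6.1 patients), total placebo risk is 20%, and the post-dose risk ratio is 0.65. All three values are assumed.
- Patients excluded: placebo (0.20 − 0.01)/0.99 = 19.2%; SNG001 0.65 × 19.19% = 12.5%; difference −6.7 points.
- Patients counted: placebo 20.0%; SNG001 0.01 + 0.99 × 0.1247 = 13.35%; difference 13.35 − 20.00 = −6.65 points.
- Events lost by exclusion: 6.1 of 305 × (0.2000 + 0.1335) = 101.7.
- Approximate power, two-sided 0.05: 62% with exclusion, 60% with counting.

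Absolute risk in both arms is understated, but the treatment difference hardly moves.

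**The case against.** The strongest reply is that the SAP never meant this. SAP 5.3.1.3 speaks of a patient randomised with a score of 5 or more, and 5.3.1.4 of one enrolled with 6 or more. Someone randomised at 4 who worsens overnight fits neither description. SAP 5.3 also opens with an allowance for other specification, and pre-treatment is the protocol's name for the Day 0 visit. This stands as evidence of intent. It does not settle the text: both sentences still turn on the score at baseline, Protocol 8.5 defines baseline by first dose without mentioning pre-treatment, and the separate SAP rule for undosed patients would be redundant if baseline were always the Day 0 score.

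Four stronger readings are tempting, and the documents do not support them.
- *The SAP certainly removes these patients and so breaks the ITT estimand.* The wording is in conflict; removal follows only on the literal reading.
- *Up to about 18 patients are lost (610 × 0.75 × 0.04 = 18.3).* That product omits the requirement that a dose follow the deterioration.
- *The result is biased towards one arm.* Deterioration before a blinded first dose cannot be caused by treatment, so exclusions should balance in expectation.
- *The per-protocol set automatically drops anyone not at 4 on Day 1, including those who improve to 3.* SAP 7.1.2 lists a baseline other than 4 among deviations that may be relevant and leaves decisions to blinded review.

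It is also fair to say that counting Day 1 pre-dose scores touches the endpoint window, which runs from first dose for dosed patients. ITT settles who is analysed, not when the window opens, so the change needs its own sentence in the SAP.

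**Conclusion.** The point holds as a conflict between text and apparent intent that should be resolved before the derivation is programmed. Read literally, the rule excludes randomised patients on a post-randomisation outcome and treats the same event differently according to later dosing. The size is unknown and probably small: about 0 to 9 of 610 under the assumed ranges, nearly all in the 5-or-more branch. The expected harm is a few lost events, slightly understated absolute risks and an undeclared departure from the protocol's estimand. Neither a directional bias nor a material loss of power is expected. The exclusion does not touch the primary endpoints or the separate death endpoint. The SAP 9.2.1.3 statement that Day 1 is always 4 is not guaranteed for next-day starters.

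**What to change.** - In SAP 5.3.1.3 and 5.3.1.4, apply the 5-or-more and 6-or-more exclusions to the last OSCI at or before randomisation. Use the same score for any per-protocol judgement that baseline was not 4.
- Keep all other randomised patients in both analyses. Count scores of 5 or more (6 or more) from the Day 1 assessment onward, and state that the Day 1 pre-dose score lies within the 35-day window.
- In SAP 9.2.1.3, correct the claim about Day 1 for next-day starters, so that their observed Day 1 score can enter the imputation model.
- List the exclusion in SAP Section 15 as a change from the protocol.

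The cost is some wording and one derivation; the Day 0 OSCI is already scheduled for every patient. The downside is that a few events preceding drug exposure are counted, which slightly dilutes the contrast (in the illustration, −6.65 rather than −6.7 points and about two points of power).
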